The results of the Outreach Methods study will be assessed as described in this document. This statistical analysis plan begins with an overview of the key components of the study, including its design, objectives, and outcomes measures. This is followed by a detailed description of the statistical analyses that will be utilized to address study hypotheses.

1. Overview of study: This study used a multi-arm randomized control trial to test the impact of automated text/telephone messages, with and without information about COVID-19 vaccine availability, on the scheduling and completion of adolescent well-care visits (AWC). We randomized eligible patients to the Standard Message group, the COVID-19 Vaccine Message group, or the Control Group. We generated random allocation sequence stratified by clinic location using block randomization (with a block size of 3). Based on sample size calculations, we planned to enroll a minimum of 859 subjects overall aged 12-17 years old that met eligibility criteria based on data obtained from the electronic health record (EHR) from three academic pediatric primary care practices.

1.1 Study Objective: Test the effectiveness of text and telephone messages, with and without information about COVID-19 vaccine availability, on the scheduling and completion of adolescent well-care visits (AWC) in adolescents due for preventative services.

Working hypothesis: Twenty percent of patients in the Standard Message group, 30% of patients in the COVID-19 vaccine group, and 2% of those in the control group will complete an adolescent well-care visit within 8 weeks.

1.2 Outcome measures

Primary

- Adolescent well-care visit completed within 8 weeks of receiving first intervention
 - Appointment completed (yes or no) based on electronic health record documentation

Secondary

- Adolescent well-care visit scheduled within 2 weeks of receiving first intervention
 - Appointment scheduled (yes or no) based on electronic health record documentation
- Adolescent receipt of COVID-19 vaccine within 8 weeks of receiving first intervention
 - COVID-19 vaccine administered (yes or no) based on electronic health record documentation
- Family member receipt of COVID-19 vaccine within 8 weeks of receiving first intervention
 - COVID-19 vaccine administered (yes or no) based on electronic health record

1.3 Time points of interest

- Scheduled adolescent well-care visit (within 2 weeks of receiving first intervention)
- Completed adolescent well-care visit (within 8 weeks of receiving first intervention)
- Receipt of COVID-19 vaccine (within 8 weeks of receiving first intervention)
- Family member receipt of COVID-10 vaccine (within 8 weeks of receiving first intervention)

1.4 Data Management

CCHMC CRC will guide data management for this project as described in the study protocol.

1.5 Interim Safety Analyses

No interim analyses are planned for this study.

2. Statistical Reports

2.1 Report Generation

2.1.1 Software

Outreach Methods SAP

Version 1.1, 1/14/22

pg. 1

All statistical analyses will be performed using SAS version 9.4 (SAS Institute Inc., Cary, NC, USA) under Microsoft Windows operating system

2.2 Analysis Populations

2.2.1 Completion

Subjects will be considered to have completed the study on the study end date on 8/5/21.

2.2.2 Missing data

We will use data obtained from patient's electronic health record (EHR) to calculate our primary and secondary outcomes. Missing outcome data could occur for several reasons, such as errors of medical documentation or the patient no longer in the primary care registry.

2.3 Statistical Report Contents

The following section outlines the contents of the final statistical analysis. For all analyses, subjects who are enrolled in the study and are eligible will be analyzed in the groups to which they were allocated.

2.3.1 Description of study population

Sample size:

The total number of subjects who are enrolled will be given.

Demographics and Clinical Characteristics, Patient and Parent:

Demographic and clinical characteristics as measured at baseline will be summarized by trial arm. Variables to be summarized are: adolescent age, adolescent sex, adolescent race, adolescent ethnicity, insurance, parent communication preference absence of past patient receipt of measles, mumps, rubella (MMR) vaccine or diphtheria, tetanus and acellular pertussis (DTaP) vaccine as a proxy for childhood vaccine refusal, and patient lifetime historical institutional no-show rate. Variables will be summarized using descriptive statistics appropriate for each type of data item.

Baseline characteristics with large differences between groups will be included in analyses as covariates.

2.3.2 Primary outcome analysis

Primary outcome: Adolescent well-care visit completed within 8 weeks of first message sent or date of randomization for the control group.

- Appointment completed (yes or no) based on electronic health record documentation

For the primary outcome, we will use a logistic regression model to examine appointment completion within 8 weeks among the three randomized groups. If participants differ in potential covariates across treatment groups, we will conduct additional analyses adjusted for these variables.

2.3.3 Secondary outcome analyses

- Adolescent well-care visit scheduled within 2 weeks of first messages sent or date of randomization for the control group.

We will use a logistic regression model to examine appointment scheduling within 2 weeks among the three randomized groups. If participants differ in potential covariates across treatment groups, we will conduct additional analyses adjusted for these variables.

- Receipt of 1st dose of COVID-19 vaccination within 8 weeks of first message sent or date of randomization for the control group

We will use a logistic regression model to examine receipt of 1st dose of COVID-19 vaccination within 8 weeks among the three randomized groups. If participants differ in potential covariates across treatment groups, we will conduct additional analyses adjusted for these variables.

- Household member receipt of 1st dose of COVID-19 vaccination within 8 weeks of first message sent or date of randomization for the control group

We will use a logistic regression model to examine household member receipt of 1st dose of COVID-19 vaccination within 8 weeks among the three randomized groups. If participants differ in potential covariates across treatment groups, we will conduct additional analyses adjusted for these variables.

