PPC	Hi, this is [Staff First Name] from PPC. [Pt first name] is due for a check up. I'll call in a day or two to help schedule that appointment or you can walk in today to have your child seen! You can also call [contact], option 1 to schedule.	Hi, this is [First Name] from PPC. I noticed that [Child's First Name] is due for a check up. Can I schedule that for your right now? Alternate script for leaving a voice message: Hi, this is [First Name] from PPC. I noticed that [Child's First Name] is due for a check up. Sorry I missed you. Please call [contact], option 1 to schedule your appointment or walk in today to have your child seen.

*Scripts have been translated into Spanish versions by Interpreter Services

Response variables (outcomes):

- Appointment **was scheduled** within 2 weeks of intervention (Y/N) (date of actual appointment may be greater than 2 weeks from intervention)
- Appointment **was completed** within 8 weeks of intervention (Y/N). Appointment completed within 8 weeks of randomization will be used for group who does not receive any intervention.
- (Primary Outcome) Receipt of MMR by 15 months of age or receipt of 2nd MMR dose by 3 months after randomization (Y/N)
- Receipt of 1st COVID vaccination (ages 12-17 years) within 8 weeks of first intervention (Y/N)
- Family member receipt of COVID vaccination in our health system within 8 weeks of first intervention

Blocking: (controlling for factors that might influence the outcome)

- Age (12-14 months, 4 years)
- Clinic location (PPC, HPC, FPC)

Personal Contacts (12-14 months & 4-year-olds) Trial:

Randomization: Eligible patient will be identified by running a report in the electronic health record (EHR). We will run this report, stratified by clinic location, and randomly assign patients into one of the four groups created by our 2 X 2 design. Groups will receive their assigned intervention in one of four successive weeks with the sequence randomly assigned (see table below).

Replication: We will conduct a total of 3 trials, repeating the randomization procedure every 4 weeks to identify children who become eligible: Weeks 1-4 = trial #1, weeks 5-8 = trial #2, weeks 9-12 = trial #3.

Outreach Methods Study Protocol & SAP

Version 1.1, 1/14/22

	1 automated message sent	2 automated messages sent
0 personal contact attempt	Message sent on Thu (weeks 3, 5, 10)	Message sent on Thu & Fri (weeks 4, 6, 12)

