1 personal contact attempt	Above plus attempt Mon – Fri of following week (weeks 2, 7, 11)	Above plus attempt Mon – Fri of following week (weeks 1, 8, 9)

MyChart and Televox Trials (6-17 years old):

Randomization: Eligible patients will be identified by running a report in the electronic health record (EHR). We will run this report, stratified by clinic location, and randomly assign patients into one of the study groups as described above. Groups will receive their assigned intervention in one of four successive weeks with the sequence randomly assigned (see table below).

We will randomize children who are eligible and implement interventions for each trial : Weeks 1-3 = Televox Trial 12-17yo, Weeks 4-7 = Televox Trial 6-11yo, Weeks 8-10 = MyChart Trial.

MyChart Trial:

	no message	1 MyChart message sent	2 MyChart messages (e.g. Mon and Thurs)
Standard Message	No intervention	Week A	Week B
Tailored Message		Week A	Week B

Televox (6-11yo) Trial:

no message	Low Tailored Message 2 automated standard messages sent (e.g. Thu, Fri) (weeks C, C)	High Tailored Message 2 automated tailored messages sent (e.g. Thu, Fri) (weeks D, D)
-------------------	--	---

Televox (12-17yo) Trial:

no message	Low Tailored Message 2 automated tailored messages sent (e.g. Thu, Fri) (week A)	COVID Tailored Message 2 automated messages sent (e.g. Thu, Fri) (week B)
-------------------	--	---

Of note, automated messages and/or personal contact attempts will not be completed if the parent schedules an appointment after being randomized but before receiving the intervention.

Covariates for logistic regression: (factors that might influence the outcome if not balanced across groups)

1. Child age at the time of randomization (rationale: visits are less frequent for children age 4 years)
2. Parent preference for call vs. text mode of contact (rationale: calls may be more likely to get blocked than texts)
3. Parent with activated MyChart account (Y/N) (rationale: not dependent on calling scheduling center to make appointment)

4. Access to appointment: Number of days to 3rd next available appointment at patient's clinic at time their first automated message is sent
5. Patient receipt of any past immunizations (Y/N) (rationale: vaccine refusing parents will be unlikely to change even if they return for well child check)
6. School-age vs. adolescent patient age (rationale: adolescents less likely to get yearly check-ups)
7. Historical no-show rate

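### Outcome windows have equal length but open at randomization for controls and at the first message for message arms, so contrasts cover different calendar days

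*Combined protocol and SAP*

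**What the plan says.** SAP 2.3.2 defines the primary outcome as "Adolescent well-care visit completed within 8 weeks of first message sent or date of randomization for the control group". SAP 2.3.3 uses the same split for the secondary outcomes, for example "Adolescent well-care visit scheduled within 2 weeks of first messages sent or date of randomization for the control group" and "Receipt of 1st dose of COVID-19 vaccination within 8 weeks of first message sent or date of randomization for the control group"; the household-member vaccination outcome follows suit. SAP 1.2 and 1.3 count from the first intervention and give no rule for controls, so 2.3.2 and 2.3.3 govern.

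The protocol's list of response variables has the same rule for completion: "Appointment completed within 8 weeks of randomization will be used for group who does not receive any intervention". It gives no control start date for scheduling or vaccination.

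On timing, the protocol section on the MyChart and Televox trials states: "Groups will receive their assigned intervention in one of four successive weeks with the sequence randomly assigned". The slot for this trial is "Weeks 1-3 = Televox Trial 12-17yo". The low tailored (standard) arm is placed in week A and the COVID arm in week B, with Thursday and Friday as example days. The same section says that outreach is not carried out "if the parent schedules an appointment after being randomized but before receiving the intervention".

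No date of randomization relative to weeks A and B is given. The SAP names no common start date, control index date or calendar-time adjustment.

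**The concern.** Randomization makes the arms comparable from the day of randomization, over the same days. Here, bookings, visits and first vaccine doses between randomization and the first message are counted for controls but fall outside the message-arm window. At the other end, the last days of the message-arm window have no counterpart in controls. Because weeks A and B differ, the standard and COVID message arms are also compared over different days.

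Any trend in background booking or vaccination then enters the contrast as if it were a message effect. A rising trend flatters the messages and a falling one hides their benefit. The protocol itself treats calendar conditions as possible influences: its covariates include a 7-day moving average of community COVID rates and days to the third next available appointment.

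For events that happen only once, such as a first dose, there is a smaller effect even without a trend. The message arm loses those who have the event in the gap.

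**Working it through.** **Inputs.** From the documents: windows W = 14 and 56 days; a 3-week slot; Thursday as the example first-send day; SAP minimum of 859 in three arms, so 859/3 = 286.3 per arm (equal allocation inferred from the block size of 3); planned 8-week completion of 2% in controls and 20% and 30% in the message arms. Assumed: one randomization on the Monday of week 1; first message on the Thursday of week 1, 2 or 3, so lag L = 3, 10 or 17 days; background rates other than 2%; background hazard changing by 10% per week.

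The plan gives no figure for the lag or its effect. As background, the usual two-proportion formula for 20% versus 30% (two-sided 0.05, 80% power) gives 294 per arm, or 882, within 3% of 859. The point does not depend on this.

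**Step 1: shared days.** Overlap between message and control windows = max(0, W - L)/W.

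| First message (assumed) | L | 2-week window | 8-week window |
|---|---|---|---|
| Thursday, week 1 | 3 | 11/14 = 79% | 53/56 = 95% |
| Thursday, week 2 | 10 | 4/14 = 29% | 46/56 = 82% |
| Thursday, week 3 | 17 | 0/14 = 0% | 39/56 = 70% |

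The 2-week windows are disjoint only when L is 14 days or more.

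**Step 2: message-arm rate with no message effect.** Let H(a,b) be the cumulative background hazard from day a to day b, calibrated so that 1 - exp(-H(0,W)) equals the control rate. The message arm then shows exp(-H(0,L)) x (1 - exp(-H(L,L+W))). This takes the definition literally, so a gap event does not count in the message arm.

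Worked case: 8-week outcome, 10% in controls, hazard falling 10% per week, L = 17.
- H(0,56) = -ln 0.9 = 0.1054
- H(17,73) = 0.1054 x 0.9^(17/7) = 0.0816
- H(0,17) = 0.1054 x (1 - 0.9^(17/7))/(1 - 0.9^8) = 0.0418
- Message-arm rate = 0.959 x 0.0783 = 7.5%

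With a rising hazard it is 12.1%. At L = 10 the pair is 8.4% and 11.2%.

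**Step 3: type I error.** Normal approximation, 286.3 per arm. In the worked case the standard error is sqrt((0.10 x 0.90 + 0.075 x 0.925)/286.3) = 0.0236, and the shift of 0.0249 is 1.05 standard errors. The chance of p < 0.05 is Φ(-1.96 + 1.05) + Φ(-1.96 - 1.05), about 18%.

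| Outcome and control rate | L = 3 | L = 10 | L = 17 |
|---|---|---|---|
| 8-week, 10% | about 5% | 8-10% | 13-18% |
| 2-week scheduling, 5% | about 5% | 6-8% | 8-12% |

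Ranges span a rising and a falling hazard. Higher background rates give more: 2-week scheduling at 10% with a falling hazard gives about 13% at L = 10 and 26% at L = 17.

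**Step 4: flat hazard.** The message-arm rate is the control rate times exp(-hL).
- 8-week outcome at 10%: h = 0.1054/56 = 0.00188 per day; at L = 17, 10% x exp(-0.032) = 9.7%, which is negligible.
- 2-week scheduling at 10%: h = 0.1054/14 = 0.00753 per day; at L = 17, 10% x exp(-0.128) = 8.8%.

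**Step 5: primary outcome at the planned 2%.** At L = 17 the message arm would show 1.5% (falling) or 2.5% (rising), a shift of at most about 0.5 points. The planned differences from control are 20 - 2 = 18 and 30 - 2 = 28 points.

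**The case against.** **Equal length.** A reader might infer that one arm is observed for longer. The documents do not support that: every arm has 14 or 56 days, and only the start date differs. Equal length does not make the days the same, so the point stands in that form.

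**Unknown lag.** Weeks A and B are undefined, and randomization could have come just before the first send. If A and B are weeks 1 and 2, the assumed lags are 3 and 10 days and the 2-week windows still overlap. A reader might conclude that the scheduling windows do not overlap at all; that needs a lag of 14 days or more, which the 3-week slot allows but the text does not state. At a lag of 3 days the harm is close to nil. Still, with A and B in different weeks, both message arms cannot share the controls' start date.

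**Gap events.** The SAP does not say how a dose or booking between randomization and message is scored. That it counts as No in the message arm is the literal reading of the definition, not a stated rule. The silence is itself a gap in the plan.

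**Covariate adjustment.** The protocol allows adjusted analyses with community COVID rate and appointment access as candidates. This is weak protection. It is conditional on imbalance, these variables would be almost determined by arm, access is measured at the first automated message (which controls do not have), and the SAP's baseline list contains neither.

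**Conclusion.** The concern holds as a difference in start dates. As written, the SAP compares message arms with controls, and the message arms with each other, over different calendar days, and nothing in it corrects for that.

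The size depends on two things the documents do not give: the lag and the background trend. At a 3-day lag the effect is negligible. At 10 to 17 days with a 10% per week trend, type I error rises to roughly 8-18% for an 8-week outcome at 10% uptake, and to 6-12% for 2-week scheduling at 5%. With no trend, the 8-week outcomes are almost unaffected at these rates; scheduling at 10% and a 17-day lag is not.

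A reader might take this to undermine the primary result. The plan's own figures do not support that: a shift of at most about 0.5 points is small against planned differences of 18 and 28 points. The exposure is mainly in the scheduling and COVID-vaccination secondary outcomes.

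**What to change.** In SAP 2.3.2 and 2.3.3, and in the protocol's outcome list for the MyChart and Televox trials, use one window for all arms of a trial.

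- Day 0 is randomization for everyone, whether or not a message was sent.
- The window closes on one common date: 2 weeks (scheduling) or 8 weeks (completion, vaccination) after the last arm's scheduled first send. If the last lag is 10 days, the windows are 14 + 10 = 24 and 56 + 10 = 66 days; if 17 days, 31 and 73.
- Count all events in that window identically in every arm, with one outcome per adolescent. The three-group logistic model is then unchanged, and adolescents whose message was withheld have a defined outcome.
- State the actual randomization and send dates.
- Report the message-anchored definition as a sensitivity analysis.

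Giving controls a separate index date for each message week is less suitable. Each control would have two outcome values, the single three-group model would not fit, and the two message arms would still be compared over different days.

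**Cost.** Wording and a re-cut of EHR dates; no new subjects. The closing date is no later than the one the plan already needs for the last-sent arm. Pre-message events are counted equally in all arms, which dilutes the contrast. With a flat hazard and a 17-day lag, a 2% control completion rate becomes 1 - 0.98^(73/56) = 2.6%, which is minor; 5% scheduling becomes 1 - 0.95^(31/14) = 10.7%, which is more noticeable. The earlier-sent arm also has somewhat longer follow-up after its message. The SAP is dated 1/14/22, after the 8/5/21 study end date in its section 2.2.1, so the change should be dated and both definitions reported.
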